7.6 Handling missing data

Missing data will not be imputed in this study. For summary statistics and concentration-time profiles, all values that are below the limit of quantitation will be set to zero.

7.7 Baseline and demographic characteristics

Subject baseline characteristics; including demographics, medical history, physical examination, ECG, and vital signs will be summarized descriptively. The descriptive statistics, including n (number of observations or sample size), mean, standard deviation and/or standard error, median, range (minimum-maximum), geometric means and geometric

coefficient of variance (where applicable) for numerical variables, and frequency and percentages for categorical variables, will be presented.

7.8 Safety analyses

The primary analysis of safety will be a comprehensive evaluation of AEs and/or toxicity, presented by dose, regimen and tumor type cohort and overall, based on:

- The type, incidence, severity, timing, seriousness, and relatedness of adverse events.
- Incidence of DLT and TEAEs that led to treatment modification
- Recording of IRR, CRS and CLS
- Results of monitoring vital signs (BP, HR, RR and body temperature)
- Results of clinical chemistry, hematology, thyroid function, coagulation, and urine analysis tests
- ECG results
- Changes in physical examination
- Results of immunogenicity assessments ADA and NAb
- Need for concomitant medications

All safety analyses will be descriptively summarized based on the safety population.

AEs/SAEs will be coded and tabulated using the current version of MedDRA. Each AE will be classified by system organ class and preferred term. All AEs along with the coded terms will be listed.

7.8.1 Safety data handling

Adverse events

All AEs will be coded according to MedDRA and graded for severity using the CTCAE v.5.0.

Treatment-emergent adverse events (TEAEs) and treatment-emergent serious adverse events (TESAEs) are defined as those AEs/SAEs that occurred or worsened at or after the start of the first infusion of the first study drug. The occurrence of TEAEs and TESAEs will be reported up until the STFU Visit.

Only TEAEs and TESAEs will be summarized. The incidence of TEAEs will be presented using the number and percent of subjects who experienced the AE using MedDRA (overall incidence, System Organ Class and preferred term) and the worst CTCAE grade. The incidence of the following TEAEs and drug-related TEAEs will be summarized by treatment group / cohort: Overall, TEAEs leading to dose interruption, dose delay, dose reduction, permanent discontinuation, IRR, CRS, and CLS. The TESAEs will be summarized similarly.

Individual listings of DLTs will be presented by MT-3724 dose cohort in Part 1, with the AE term, MedDRA terms, treatment cycle of onset, serious or non-serious and severity grade (CTCAE v.5.0) provided for each DLT.

The pre-treatment AEs include those AEs that occurred due to study-related procedures. These AEs will be assessed by verbal probes and from medical history. The pre-treatment AEs will be listed by subject but not summarized.

Laboratory safety tests

Laboratory results will be summarized by treatment group/cohort using absolute values and change from baseline; or presented as per-subject listings. The incidence of laboratory data outside the reference range (L, H) will be summarized in frequency tables by treatment group/cohort. Further details will be provided in the SAP.

Physical examination

The overall results of the physical examination ('normal', 'abnormal, NCS', or 'abnormal, CS') will be summarized by treatment group/cohort and listed per subject. Comments for abnormal CS results will be listed.

Other safety variables

Quantitative data for other safety variables will be summarized by the following descriptive statistics: arithmetic mean, standard deviation, median, minimum, and maximum. These summary statistics will be presented by the treatment group/cohort for the absolute values and changes from baseline. Frequency tables will be provided for qualitative data.

Results of VS (body temperature, systolic blood pressure, diastolic blood pressure, respiratory rate, and heart rate) will be summarized by the descriptive statistics listed above.

ECG results (HR, PR, QRS, RR interval, QT, QTcF, and the results of the overall ECG review by the investigator) will be summarized by the descriptive statistics listed above. Comments for abnormal CS results of the ECG will be listed.

All prior and concomitant medications will be assigned a generic name and a drug class based on the World Health Organization Dictionary. Prior and concomitant medications will be listed and summarized by treatment group/cohort and (if appropriate) by drug class.

7.9 Efficacy analyses

The statistical analysis of efficacy variables will be performed on the safety population.

Tumor assessment will be performed by the FDG-PET-CT scan in subjects with FDG-avid NHL histology along with CT or MRI to capture measurements, wherever possible, and by the CT or MRI scan in subjects with low or variable FDG avidity. The investigator at each site will determine the ORR at each time point based on the radiologist's measurement of all evaluable lesions.

The investigator at each site will determine the objective tumor response (OR) using the 5PS per the Lugano Classification for Lymphoma ([Cheson 2014](#)) adjusted according to LYRIC (lymphoma response to immunomodulatory therapy criteria) ([Cheson 2016](#)). An overview of LYRIC is presented in [Appendix 3](#). The BORR of all time points will be reported. Subjects

who experience disease progression before undergoing the first tumor assessment will be added to the disease progression stratum. The BORR will be descriptively summarized by the treatment group/cohort; the exact 95% confidence intervals will also be produced.

The ORR representing clinically significant clinical benefit in this study will comprise the Lugano Score 1, 2 or 3, or the CR or PR. All subjects achieving clinically significant clinical benefit according to both response criteria will be included in the analysis of the DOR. DOR is defined as the time from the first documented complete or partial response to the actual date of disease progression or death before progression. The PFS will be defined as the time from the start of treatment with MT-3724 on C1D1 to the date of disease progression or death from any cause. Subjects who have not progressed or died at the time of data base lock will be censored at the date of their last tumor assessment. The DOR will be descriptively summarized by the treatment group/cohort; the exact 95% confidence intervals will also be produced.

The DCR will be defined as the percent of subjects with objective response of CR, PR or stable disease (SD, defined as SD for 6 months or longer). The DCR will be analyzed using similar methods as the ORR. Further details will be provided in the SAP.

A detailed description of analysis methods will be provided in the SAP to be completed before the EoT Visit in the last subject.

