3.3.1 MT-3724

MT-3724 will be administered as an IV infusion over 1 hour (54 to 75 minutes).

Treatment with MT-3724 will be administered for cycles of 28 days each until death, disease progression, unacceptable toxicity, withdrawal of consent or another reason for withdrawal, or until study discontinuation.

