6.6 Efficacy assessments: Radiological Assessment of Tumor Response

The tumor response assessment should be performed at the following time points:

- At Screening:
 - The investigator is encouraged to obtain the screening tumor scan as close as possible to the start of treatment within 28 days of C1D1.
- Within 7 days before the start of treatment on C3D1 and every other cycle thereafter (i.e. Between D23 and D28 of the cycle). The original schedule needs to be maintained even if there is a delay in dosing.
- Within 7 days of the EoT Visit (**only** if the previous tumor scan has been performed >4 weeks before the EoT Visit)

The investigator and the radiologist should carefully consider if the increase from baseline in tumor size could be “pseudoprogression” due to the tumor flare induced by the study drug(s).

Unscheduled tumor response assessment by FDG-PET-CT (or CT/MRI, where applicable) may be ordered at the investigator’s discretion.

Efficacy of the study drugs (tumor response) will be assessed by the scan of all anatomic regions involved with the measurable disease. Positron emission tomography-computed tomography should be used in subjects with FDG-avid tumor histology. Computed tomography or MRI should be used in subjects with tumor histology of low or variable FDG avidity. Diagnostic quality CT should be collected for all subjects at baseline, whenever possible.

Tumor response in subjects with FDG-avid tumor histology will be determined using the 5-point scale (5PS) according to the Lugano Classification for Lymphoma ([Cheson 2014](#)) adjusted according to LYRIC (lymphoma response to immunomodulatory therapy criteria) ([Cheson 2016](#)). An overview of NHL response criteria for FDG avid and non-avid NHL is presented in [Appendix 3](#).

The same technique (e.g. slice thickness, field of view) should be used for all scans during the study treatment period. Preferably, all scans should be interpreted by the same investigator during the study whenever possible. Scans must meet the SOC for imaging of lesions in the respective organ system(s).

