6.1.4 Progression-free Survival

Progression-free survival (PFS) is the time from study drug administration until disease progression or death. The disease assessment by the RECIST V1.1 criteria occurs at Screening, months 1, 3, 6, 9, 12, 18 and 24.

PFS is defined as the interval between the date of first infusion of and the date of PD or death, whichever is first reported.

PFS (days) =

Date of Progression – Date of 1st Infusion + 1

The following Kaplan-Meier (KM) estimates will be provided:

- 25th, 50th (i.e., median) and 75th KM percentiles with 95% CIs
- Number and percent of subjects censored/not censored

KM estimates of the proportion of subjects event-free at: 3, 6, 12, 18, and 24 months (note: not all estimates may be provided for interim analyses)

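### The 3-month PFS landmark and the 6-month stable-disease condition in DCR fall between the protocol's scheduled scans, and the SAP assumes a different assessment schedule

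*Protocol*

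**What the plan says.** - **Scan times.** Protocol 6.6 schedules tumor assessment "Within 7 days before the start of treatment on C3D1 and every other cycle thereafter (i.e. Between D23 and D28 of the cycle", and adds: "The original schedule needs to be maintained even if there is a delay in dosing". Protocol 3.3.1 sets the cycle length: "Treatment with MT-3724 will be administered for cycles of 28 days each". The scan days are therefore fixed to the calendar. Section 6.6 also allows unscheduled scans. It asks for an end-of-treatment (EoT) scan when the previous one is more than 4 weeks old.
- **DCR.** Protocol 7.9 defines it as the share of subjects with CR, PR or "stable disease (SD, defined as SD for 6 months or longer". The duration condition is attached to SD only; CR and PR carry none. No start date, month-to-day rule or scan window is given. The section continues: "The DCR will be analyzed using similar methods as the ORR. Further details will be provided in the SAP". The readable SAP text does not mention DCR. The added exploratory endpoints in SAP section 4 are blacked out, so nothing here rests on DCR being absent.
- **PFS.** SAP 6.1.4 plans "KM estimates of the proportion of subjects event-free at: 3, 6, 12, 18, and 24 months". The same section says disease is assessed by RECIST V1.1 at screening and at months 1, 3, 6, 9, 12, 18 and 24. Protocol 6.6 and 7.9, and the SAP's own objective response section (6.1.1), use Lugano with the LYRIC adjustment.

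**The concern.** Progression found by imaging is dated when a scan finds it. If a landmark lies well after one scan and before the next, subjects who progress in the gap still count as event-free, so the proportion is too high. If a duration threshold lies between two scans, whether a subject meets it depends on the time origin chosen and on whether a later scan exists, not only on the disease.

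Two results are exposed: the 3-month PFS proportion (PFS is a listed secondary endpoint) and the SD component of DCR. Both are likely to be set beside published lenalidomide-rituximab results such as those in protocol 1.3.1.

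**Working it through.** **Scan windows (Day 1 = C1D1).** Scans fall on D23-D28 of each even cycle c, that is Days 28(c-1)+23 to 28c. One month is taken as 30.4375 days.

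| Cycle | Days | Months |
|---|---|---|
| 2 | 51-56 | 1.7-1.8 |
| 4 | 107-112 | 3.5-3.7 |
| 6 | 163-168 | 5.4-5.5 |
| 8 | 219-224 | 7.2-7.4 |

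Three months is 3 x 30.4375 = Day 91, between Days 56 and 107. Six months is 6 x 30.4375 = Day 183, between Days 168 and 219. On the SAP's schedule both would be assessment times.

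**Survival model (an assumption; the plan states no figure to reproduce).** Exponential, S(t) = 0.5^(t/median), with the 3.7-month median PFS that protocol 1.3.1 gives for lenalidomide plus rituximab:

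- S(54) = 0.717, S(91) = 0.571
- S(165) = 0.362, S(183) = 0.324, S(221) = 0.257

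**3-month PFS.**
- If progression is seen only at scheduled scans, the Day 91 estimate carries status from about Day 54: 72% against a true 57%, a difference of 0.717 - 0.571 = 0.146.
- For medians of 6.0 and 2.5 months the difference is 0.815 - 0.708 = 0.107 and 0.611 - 0.437 = 0.174.
- Now let a share f of the hazard be seen in real time, through deaths, EoT scans or unscheduled scans. The reading becomes S(54) x exp(-f x (ln 2/3.7) x (91-54)/30.4375), which is 0.701 for f = 0.1 and 0.670 for f = 0.3. The excess is then about 10 to 13 points.

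**SD component of DCR.** Assume 67% non-responders (100% minus the 33% response rate in protocol 1.3.1) with the same hazard.
- A scan at or after 6 months required, met at cycle 8: 0.67 x (0.324 - 0.257) = 0.045 too low.
- SD at the cycle 6 scan accepted: 0.67 x (0.362 - 0.324) = 0.025 too high.
- In 40 Part 2 subjects these are about 40 x 0.045 = 1.8 and 40 x 0.025 = 1.0 subjects.

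**Effect of the origin.** The baseline scan may be up to 28 days before C1D1. Timed from a scan 1-28 days before C1D1, the cycle 6 scan falls 163-195 days later (5.4-6.4 months). It passes 182.6 days if the baseline scan was at least 16 to 21 days before C1D1, depending on the day within the cycle 6 window.

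**The case against.** **The SAP has its own schedule and claims precedence.** SAP section 4 puts its statistical methods above the protocol's, and its months 3 and 6 are assessment times. But when scans are taken is trial conduct, which protocol 6.6 governs, and SAP Appendix A is only a placeholder for the protocol's schedule. The landmarks therefore rest on a schedule that the sites will not follow. The objection shows that the conflict between the schedules comes first and must be settled.

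**A reader might infer that DCR needs about 7.3 months of verified disease control.** The documents do not support that. CR and PR count without any duration. For SD the origin is unwritten: timed from the baseline scan, or with 6 months read as 24 weeks (168 days), the cycle 6 scan can qualify. An EoT scan can also supply later evidence. After a cycle 6 scan it is called for when the EoT visit is more than 4 weeks later, so at Day 192 or after; a scan within 7 days of that visit is at Day 185 or after. Protocol 3.5 continues radiology follow-up after treatment for subjects with CR, PR or SD.

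**A reader might infer that 3-month PFS is simply Day 54 status.** It is not. Deaths, EoT scans and unscheduled scans also count, so 72% is a ceiling.

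**Interval detection is common to all imaging-based PFS, and little depends on these figures.** Both are fair. The study has no power calculation (protocol 7.3), and DCR is not among the listed primary or secondary endpoints (the exploratory rows are blacked out). That limits the harm to interpretation. It does not justify a landmark five weeks after the only scheduled scan that informs it.

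**Conclusion.** The point holds in a limited form. Under the protocol's schedule, the 3-month landmark and, timed from C1D1, the 6-month SD condition fall between scheduled scans, and the SAP's schedule and response criteria contradict the protocol's.

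- **3-month PFS:** about 10 to 15 points too high at a 3.7-month median. The upper end applies if only scheduled scans detect progression; the lower end if 30% of the hazard is seen in real time.
- **SD component of DCR:** about 4.5 points too low or 2.5 too high against 6-month control, depending on which scan is accepted. As written, the same subject can pass or fail according to the origin used and whether a later scan exists.

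These sizes rest on exponential PFS, a reference median and response rate from another regimen, and an equal hazard in non-responders. A 7-point DCR effect is tempting, since 0.67 x (0.362 - 0.257) = 0.070, but that compares the cycle 6 scan with the cycle 8 scan, not either one with 6 months. No error rate or power is affected.

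**What to change.** 1. In SAP 6.1.4, replace the schedule and RECIST V1.1 sentence with the protocol 6.6 schedule and Lugano/LYRIC.
2. Report Kaplan-Meier event-free proportions just after scheduled scans, for example Days 60, 116, 172 and 340 (after the cycle 2, 4, 6 and 12 windows; cycle 12 is Days 331-336). Alternatively, keep 3 months and label it as reflecting the cycle 2 scan.
3. In protocol 7.9 and the SAP, define durable SD from C1D1 as SD at the third scheduled assessment (Day 163 or later) with no earlier PD, and describe it as about 24 weeks.

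**Cost.** Wording only, with no extra scans. The landmarks are not round months and so are harder to set beside published figures. Day 340 is on the scan grid only for subjects still on treatment. The durable-SD cut is slightly under 6 months and, on the assumptions above, reads about 2.5 points above true 6-month control. In exchange the rule is the same for every subject.

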5.6 Blinding

Not applicable; this is an open-label study.

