7.2 General statistical considerations

Statistical analysis will be performed using the Statistical Analysis System®; the version used will be specified in the statistical analysis plan (SAP).

All data will be listed, and descriptive summary tables will be provided by treatment group/cohort irrespective of the study part. In addition, appropriate variables will be summarized in a separate treatment group comprising the subjects treated at the MTD of MT-3724 in Part 1 (dose escalation) and in Part 2 (expansion). These variables will be specified in the SAP.

Quantitative data will be described by the following summary statistics: arithmetic mean, standard deviation, median, minimum, and maximum. Where appropriate, descriptive summary statistics will be tabulated for the absolute values and changes from baseline. Graphical illustrations will be provided where appropriate. Qualitative data will be presented in the frequency tables.

The assessment obtained at the most recent time before the start of MT-3724 treatment will be the baseline for all post-baseline assessments. The value obtained before MT-3724 Dose 1 on C1D1 (if available) will serve as the baseline; if not available, then the value obtained earlier at screening will serve as the baseline.

Further details about the statistical analyses will be provided in the SAP. Any changes in the statistical methods described herein compared to the final SAP will be documented in the integrated clinical study report.

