7.13 Interim analysis

No formal interim statistical analysis is planned during either part of this study. A formal interim statistical analysis may be performed only pursuant to a health authority request.

Informal (preliminary) statistical analyses may be performed at sponsor's discretion at any time during the study. These analyses would be performed without the interim data base lock for the purposes of the IB update, safety reports to the health authorities (e.g., data safety update report), meetings with health authorities or for internal decisions.

In addition, data from individual subjects and cohorts will be reviewed without formal statistical analysis on an ongoing basis during the study (e.g. to support the dose escalation decisions in Part 1).

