7.14 Protocol deviations

Protocol deviations are defined as deviations from the procedures outlined in the protocol. Major protocol deviations are those deviations that could have an impact on subject's safety or on the ability to interpret the study results.

Deviations from the protocol should not occur. If a deviation occurs, the investigator must immediately inform the monitor, and the implications of the deviation must be reviewed and discussed with the sponsor. Deviations should be reported to the IRB/EC per local requirements.

The impact of the protocol deviations on data quality and integrity will be re-assessed after the completion of the study conduct (last visit by the last subject) and before the data base lock. All decisions regarding the type of deviations (major or minor) will be made prior to commencing the final analysis on the final locked database. Major protocol deviations may lead to exclusion of data from analysis. A listing of all major protocol violations will be presented in the final study report.

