4. CHANGES TO PLANNED ANALYSIS

The statistical methods described in this SAP take precedence over the protocol. Additional exploratory efficacy endpoints have been added.

- [REDACTED]
- [REDACTED]

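### The SAP may be completed just before the last subject's end-of-treatment visit and overrides the protocol, so secondary efficacy rules can be replaced after much of the Part 2 response data has been seen

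*Protocol*

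**What the plan says.** Four provisions have to be read together.

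- **Deadline.** Protocol 7.9: "A detailed description of analysis methods will be provided in the SAP to be completed before the EoT Visit in the last subject". Protocol 5.8 sets no maximum number of cycles, so the last subject's visit has no fixed date.
- **Visibility.** Protocol 5.6 on blinding: "Not applicable; this is an open-label study". Under 7.9, response is read by the site investigator.
- **Informal looks.** Protocol 7.13: "Informal (preliminary) statistical analyses may be performed at sponsor's discretion at any time during the study". No interim lock is needed, and the listed purposes end with "meetings with health authorities or for internal decisions". SAP 9 repeats the permission.
- **Precedence.** SAP 4: "The statistical methods described in this SAP take precedence over the protocol".

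Two provisions work the other way. Protocol 7.9 itself defines ORR, DOR, PFS and DCR and gives a censoring rule for PFS. Protocol 7.2 adds: "Any changes in the statistical methods described herein compared to the final SAP will be documented in the integrated clinical study report".

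**The concern.** In a single-arm, unblinded trial, freedom from bias in ORR, DOR and PFS rests largely on their rules being settled before the results are seen. Here the sponsor could summarise Part 2 response data, then complete or reissue an SAP that alters the response set, the censoring or the pooling, and comply with every sentence of both documents.

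A reissue is to be expected. SAP 3.1 and 3.2 describe three planned cohorts where Protocol 3.6 lists five. SAP 5.3 has a 28-day screening window where Protocol 3.2 has 35 days for most procedures. SAP Appendix A is still a placeholder. The late deadline would therefore apply to a revision that has to be made.

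At stake is the credibility of the Part 2 efficacy figures. The Synopsis lists efficacy among the things Part 2 is to confirm. Protocol 3.7 and SAP 3.1 name only safety and tolerability there and treat tumor response as something to evaluate further.

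**Working it through.** **1. The plan's own figure.** Protocol 7.3 plans 24 subjects in Part 1 and about 40 in Part 2: 24 + 40 = 64. No power, alpha or effect size is stated, so there is no power calculation to reproduce.

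**2. Do the two documents already differ on efficacy rules?** The SAP subsections cited are printed as 6.1.3 and 6.1.4, under SAP 7.2.

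| Rule | Protocol | SAP |
|---|---|---|
| DOR set | Subjects with clinical benefit, framed by Lugano score 1 to 3 or CR/PR (7.9) | Adds CRu, which Appendix 3 of the protocol does not contain, and stable disease of at least 3 months (6.1.3) |
| DOR end | Progression, or death before it (7.9) | Formula uses the progression date only (6.1.3) |
| DOR after missed evaluations | No such rule | Death or progression after more than one missed evaluation is censored (6.1.3) |
| PFS criteria and schedule | Lugano with LYRIC; scans before C3D1 and every other cycle after that (6.6, 7.9) | RECIST V1.1 at screening and months 1, 3, 6, 9, 12, 18 and 24 (6.1.4) |

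The SAP is also inconsistent with itself. It admits stable disease to the DOR analysis, then sets DOR to missing without CR, CRu or PR. Its DOR formula omits death, but a censoring bullet mentions it. Counting fewer deaths as events would generally lengthen the DOR estimate. The documents contain no data from which to say by how much.

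**3. How much could be visible at the deadline?** It depends on what the last subject means.

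*Last to reach the visit.* Everyone else has ended treatment: 63/64 = 98.4% overall, 39/40 = 97.5% in Part 2. These are counts of ended treatments, not of final outcomes.

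*Last enrolled.* This needs assumptions, so it is an illustration only:
- 40 Part 2 subjects, with uniform accrual over an assumed 6 to 24 months;
- exponential PFS with median 3.7 months, borrowed from the lenalidomide-rituximab study in Protocol 1.3.1, so the rate is ln 2 / 3.7 = 0.187 per month;
- end of treatment taken as the time of progression, and the deadline as that time for the last-enrolled subject;
- 4,000 simulated trials for each accrual length.

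| Accrual (months) | Other subjects with a PFS event: mean | 10th percentile | Past day 56, the end of the first scan window: mean |
|---|---|---|---|
| 6 | 69.5% | 43.6% | 94.6% |
| 12 | 79.8% | 61.5% | 96.9% |
| 18 | 85.1% | 71.8% | 97.6% |
| 24 | 88.8% | 76.9% | 98.1% |

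The last column is a calendar count over all 40 subjects, whether or not still on treatment.

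**4. What could one late rule move?** Assume 13 responders. Over 40 subjects, 13/40 = 32.5% (exact 95% CI 18.6% to 49.1%). If a later SAP moved to an evaluable set of, say, 34, then 13/34 = 38.2% (22.2% to 56.4%), a shift of 5.7 percentage points. Both counts are assumed. Both documents now base efficacy on the safety population (Protocol 7.4.1 and 7.9; SAP 5.2 and 7.2), so this shows sensitivity and is not a planned change.

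**5. Do the safeguards close the gap?** Protocol 7.2 asks for protocol-to-final-SAP changes to be documented in the study report. It does not ask that they be dated against informal analyses or labelled post hoc. Protocol 7.14 has deviations classed before the final analysis but after study conduct has ended, and adds: "Major protocol deviations may lead to exclusion of data from analysis". Neither fixes endpoint rules before results are seen.

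**The case against.** The strongest reply is that much is already fixed. Protocol 7.9 sets the response criteria, the exact intervals, the analysis population, the endpoint definitions and PFS censoring. What it defers to the SAP is detail of method. A late departure would have to appear in the study report. The trial is descriptive (7.3), efficacy is secondary, and an SAP already exists. All of this stands, and it rules out several stronger readings that a reader might infer.

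- *That the efficacy endpoints have no protection.* They are predefined. The weakness is that SAP 4 lets those definitions be displaced.
- *That 63 of 64 results would be known.* That is a worst-case count of ended treatments under one reading of the deadline. Protocol 3.5 continues follow-up for up to 18 months after the last MT-3724 dose, so OS, and PFS or DOR in subjects who stop without progression, can still be open.
- *That DLT or MTD findings could be rewritten.* DLT rules sit in Protocol 3.6 and Appendix 4 and are applied as data arrive. The MTD must be declared before Part 2 starts (3.7). SAP 8.2.7 only tabulates and lists DLTs.
- *That type I error is inflated.* No efficacy hypothesis is tested.
- *That rules were in fact set late.* The SAP's date is not visible and its list of changes is redacted. The documents show what is permitted, not what happened.

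The reply does not remove the core. Disclosure afterwards is weaker than fixing the rules beforehand, and the present SAP shows that the precedence clause has real conflicts to act on.

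**Conclusion.** The point holds in bounded form. The documents permit secondary efficacy rules to be replaced after much of the Part 2 response data has been seen, and the DOR and PFS rules already conflict. The consequence is possible bias in descriptive estimates of response, DOR and PFS. Its size cannot be computed from the documents.

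The amount visible at the deadline depends on the reading: at most 39 of 40 Part 2 treatments ended, or on average 70% to 89% of the other subjects with a PFS event under the assumed accrual and the borrowed 3.7-month median. The statement fits response and best response better than OS or late DOR. It is worth correcting before Part 2, because the correction is cheap and a revision is due anyway.

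**What to change.** **Protocol 7.9.** Replace the deadline with wording such as: *The SAP will be finalised and dated before the first Part 2 subject is dosed, and at the latest before any Part 2 efficacy data are summarised. Later changes will be versioned, dated against any informal analysis, and reported as post hoc in the clinical study report.*

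**SAP 4.** Limit precedence to analysis detail, so that the protocol's efficacy endpoint definitions govern where the two differ. Before that, clarify the protocol's own DOR set. It asks for benefit on both sets of response criteria, but in Appendix 3 a PET-based partial response carries a score of 4 or 5, so a literal reading excludes every such responder. Then bring SAP 6.1.3 and 6.1.4 into line on the DOR set, DOR events, missed evaluations, and PFS criteria and schedule.

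**Separately.** Protocol 3.6.1 and SAP 5.4 differ on which subjects are evaluable for dose decisions. They must be reconciled by those responsible; this point does not say which is right, and the precedence wording should not be used to settle it.

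**Cost.** The SAP revision is done earlier, a few sentences change in 7.9 and SAP 4, and a dated log of SAP versions and informal analyses is kept. No added subjects, visits or data are needed.
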